## 7.2 Administration of Study Intervention

### 7.2.1 Study Intervention

Since the clinic of dermatology is located in the circle and not anymore in the main campus of the University Hospital of Zurich, the study intervention on day 0 is at the circle.

The following visits can be done at the main campus at the department of Infectious Diseases.

Details of study Intervention	Justification
1. Inguinal skin scraping before PDT	Baseline microbiome data
2. Photosensitizer application, followed by PDT (1x)	Treatment to reduce colonization bacteria
3. Skin scraping, skin antisepsis in the groin, skin scraping after antisepsis	To measure bacterial colonization after PDT – before and after skin antisepsis

### **7.2.2 Modification of Interventions**

Trial is not modifiable

### **7.3 Compliance with Intervention**

There will be no compliance problem of the study participant since the intervention takes place at the visits. No intervention by the participant is needed except reporting of adverse effects.

### **7.4 Data Collection and Follow-up for Withdrawn Participants**

Not applicable

### **7.5 Concomitant Intervention(s)**

Since we only include participants for our analysis who do not take antibiotics or NSAR in the 14 days prior to the photodynamic treatment or until follow-up at 14 days, we will inform on that issue at the screening and at each study visit. We will record it in our eCRF.

## 8 STUDY PROCEDURES

[figure not shown]
### 8.1 Table of Study Procedures and Assessments

**Study plan:** Effects of PDT on the human inguinal skin microbiome to improve antiseptic effect

Study tasks	Screening	Intervention Period			
		Visit			
Visits	0	1	2	3	4
	at least -7 days before visit 1	0	1 (within 24 hours)	3	5
1. Participant information and informed consent	√				
2. Inclusion- and exclusion criteria	√				
3. Demographic data	√				
4. Inguinal skin scraping before photodynamic treatment		√			
5. Study intervention: PDT		√			
6. Skin antisepsis in the groin, skin scraping before and after antisepsis		√	√	√	√
7. (serious) adverse events		√	√	√	√
8. End of study information of study results					√

## Skin scrapping

For all skin swabs, we will apply the scratching method using a scalpel as described previously (Boni, Kuster et al. 2018) and illustrated below in Figure 2. The swabs will be analyzed for bacterial growth. The remaining sample will be immediately frozen at -80C° for later molecular analysis such as metagenomics.

**Figure 2.** Specimen collection in the groin of the hip before disinfection. Skin scrapings will be removed with sterile blades and transferred to ESwab culture swabs (Copan).  
T, musculus tensor fascia latae; Tr, trochanter

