## 2.4 Justification of Study Intervention

PDT enjoys great popularity as it is well tolerated. Therefore, we select this promising treatment to investigate an innovative strategy to improve skin antisepsis in a pilot study. If we see that we have sterile cultures after PDT and skin antisepsis without side effects, we will plan a larger prospective study based on these data.

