#### Group B (Methylene blue group)

On day 0, a skin scraping of the groin will be performed and sent for microbiological culture. Then, 5ml of the 0.01% methylene blue based photosensitizer (NF-031) will be applied for an area of 5 x 10cm in the right groin of the patient. Immediately after application, the photodynamic process will be started by irradiation of the area with 40J/cm^2 red light from a 635nm (absorption peak 670nm) emitting LED during 4 minutes.

Immediately after the PDT, skin antisepsis will be performed. Antisepsis of the skin is performed with a povidone-iodine/alcohol solution (Betaseptic®, Mundipharma, Limburg, Germany) and repeated three times for a total duration of 3 minutes to imitate standard surgical antisepsis before a hip arthroplasty surgery. Skin scraping will be repeated after the antisepsis and after 1, 3 and 5 days for bacterial cultures.

As a control group, we will take skin swabs before and after skin antisepsis without PDT on the contralateral site of all participants.

On day 5 of the study, volunteers will be seen for the last study visit to document any adverse effects.

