## Microbiology

In short, the patient's sample swabs will be streaked out onto Columbia sheep blood agar plate without antibiotics (bioMérieux, Marly-l'Etoile, France), colistin-nalidixic acid (CNA) blood agar (bioMérieux) plate for aerobic cultivation and a Brucella plate (in-house sheep blood agar plates with hemin and vitamin K1) for anaerobic cultivation using GENbag (bioMérieux). Final identification will be done by matrix-assisted laser desorption ionization-time of flight mass spectrometry spectrometry (MALDI-TOF MS) using a Bruker MALDI Biotyper. The amount of bacteria will be semiquantitative described as +, ++, +++ based on growth on agar plates. All cultured microorganisms will be stored in skim milk at -80C° for potential subsequent analysis by whole genome sequencing for analyzing the secondary outcome.

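### The plan describes no neutraliser or growth-inhibition control for the cultures, so no growth on day 0 cannot be separated from inhibition by carried-over iodine or, in group B, dye

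*Combined protocol and SAP*

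**What the plan says.** The primary outcome (section 4.1) is bacterial density and species by culture, before and after PDT and antisepsis. Section 8.1, under the heading on skin scraping, covers all samples with one method: "For all skin swabs, we will apply the scratching method using a scalpel as described previously". The caption of Figure 2 adds the transfer step: "Skin scrapings will be removed with sterile blades and transferred to ESwab culture swabs (Copan". That caption illustrates a specimen taken before disinfection.

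Section 8.2.1 (Microbiology) describes plating: "sample swabs will be streaked out onto Columbia sheep blood agar plate without antibiotics", with CNA and anaerobic Brucella plates alongside. The readout is a grade: "The amount of bacteria will be semiquantitative described as +, ++, +++ based on growth on agar plates".

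On timing, section 5.2 says "Immediately after the PDT, skin antisepsis will be performed", using povidone-iodine/alcohol three times over 3 minutes, and then "Skin scraping will be repeated after the antisepsis and after 1, 3 and 5 days for bacterial cultures". Section 7.2.1 lists a further scraping between PDT and antisepsis: "Skin scraping, skin antisepsis in the groin, skin scraping after antisepsis". The table in 8.1 also has scrapings before and after antisepsis at visit 1, separate from the one before PDT. The narratives in 5.2 and 8.3.2 do not include that intermediate scraping.

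The control groin receives antisepsis but no PDT and no photosensitizer. The decision rule is in section 2.4: "If we see that we have sterile cultures after PDT and skin antisepsis without side effects, we will plan a larger prospective study".

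**The concern.** A scraping from skin that has just been treated can carry some of the agent into the swab fluid and onto the plate. If the agent goes on acting there, a viable sample reads as no growth. None of the sections on collection, antisepsis, plating or visits describes a neutraliser, a rinse, removal of dye, protection of samples from light, or a control that would reveal inhibition. Read as written, a day 0 culture without growth has two explanations that the data cannot tell apart: the bacteria were killed on the skin, or they were inhibited in the sample.

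The two residues act differently. Iodine/alcohol is applied to both groins in both groups, so its residue raises apparent sterility everywhere and shrinks any contrast between PDT and control. Methylene blue is applied to the treated groin in group B only. Section 2.1 says that it does not penetrate the stratum corneum over short periods, so it stays in the layer that is scraped. Section 2.3 describes photosensitizers as reacting with visible light. Dye residue can therefore count inhibition in the sample as an effect of methylene blue PDT. At stake is the decision to move to arthroplasty patients, which rests on sterile cultures.

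**Working it through.** **Step 1. Which scrapings are exposed** (sections 5.2, 7.2.1, 8.1 table, 8.3.3)

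| Scraping | Fresh iodine/alcohol | Fresh methylene blue |
|---|---|---|
| Day 0, before PDT | no | no |
| Day 0, after PDT, before antisepsis | no | group B, treated groin only |
| Day 0, after antisepsis | both groins, both groups | group B, treated groin: whatever antisepsis leaves |
| Days 1, 3, 5, before that day's antisepsis | none that day | none that day |
| Days 1, 3, 5, after antisepsis | yes | none that day |

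The dye asymmetry is sharpest in the second row, the sample that isolates the PDT effect. It is also the sample on which the sections disagree. The control carries no dye whether it comes from all participants (5.2) or from the first ten (7.1.2).

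**Step 2. Dye load.** From 5.2 and 8.1: 5 ml of 0.01% on 5 x 10 cm. Reading 0.01% as 0.1 mg/ml, 5 x 0.1 = 0.5 mg, and 500 micrograms / 50 cm2 = 10 micrograms/cm2. Assume 5 cm2 scraped into 1 ml of fluid with 1% to 50% of the dye retained. Then 10 x 5 = 50 micrograms, and 50 x 0.01 to 50 x 0.50 gives 0.5 to 25 micrograms/ml, against 100 applied and zero on the control side. The documents give no inhibitory concentration, so this shows exposure, not harm.

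**Step 3. Effect on ten sterile results in ten.** Section 10.2 gives no rate, effect size or power, so there is no figure to reproduce. Let p be the true culture-positive rate and s the share of truly positive samples that fail to grow. Both are assumptions. P(0 of 10 positive) = (1 - p(1 - s))^10.

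| p | s = 0 | s = 0.5 | s = 0.9 |
|---|---|---|---|
| 10% | 35% | 60% | 90% |
| 30% | 2.8% | 20% | 74% |
| 50% | 0.1% | 5.6% | 60% |

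For example, at p = 30%: 0.70^10 = 0.028, 0.85^10 = 0.197, 0.97^10 = 0.737. Even without carry-over, 0/10 leaves a two-sided 95% upper limit of 1 - 0.025^(1/10) = 30.8%.

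**Step 4. Effect on the contrast with control.** Ten per side, two-sided 0.05. The first figure is Fisher's exact test, as named in section 10. The figure in brackets is exact McNemar for paired groins, computed with the two groins independent within a person.

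*Dye residue on the PDT side only, no true effect: chance of a significant result*

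| p | s = 0 | s = 0.5 | s = 0.9 |
|---|---|---|---|
| 30% | 1.2% (0.5%) | 3.4% (1.2%) | 11.3% (3.7%) |
| 50% | 1.3% (0.9%) | 8.6% (6.0%) | 43.1% (27.2%) |
| 70% | 1.2% (0.5%) | 17.6% (14.0%) | 74.9% (65.8%) |
| 90% | 0.1% (0.0%) | 38.1% (27.4%) | 96.5% (94.0%) |

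*Iodine residue equal on both sides, true effect present: Fisher power*

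| Control vs PDT positive | s = 0 | s = 0.5 | s = 0.9 |
|---|---|---|---|
| 70% vs 10% | 66.7% | 15.7% | about 0% |
| 90% vs 10% | 95.8% | 33.1% | 0.1% |

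The second table follows from the difference shrinking by the factor (1 - s): 70 - 10 = 60 points becomes 35 - 5 = 30 points at s = 0.5.

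**The case against.** The strongest reply is that this is silence, not a stated choice. Section 8.1 defers to a published method, the culture paragraph in 8.2.1 presents itself as a summary, 8.3.2 refers to an earlier approved study, and section 12 refers to written SOPs. The flow charts are missing from the copy reviewed. A neutralising step may exist in one of these places. That stands, and it rules out some stronger statements. A reader might infer that scrapings are taken from skin still wet with antiseptic or dye, or that the swabs hold a plain medium. The documents give neither the drying interval nor the medium, so neither inference can be made. If the step exists, stating it takes a sentence.

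Second, the go criterion refers to cultures after PDT and antisepsis, and three antiseptic applications may remove much of the dye. This also stands. It confines the dye bias mainly to the earlier day 0 scraping, but it leaves the iodine question at the very sample on which the decision rests.

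Third, the figures in step 4 depend on an assumed s, and section 10.3 also calls the analysis descriptive only. They show the scale if suppression occurs, not that it does. At a true positive rate of 30%, even s = 0.9 yields few false positives.

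The planned real-time PCR does not settle the matter, because 8.2.2 does not describe it as separating viable from inhibited or dead bacteria. An enrichment broth might seem a natural addition, but it addresses low counts rather than carry-over and is not needed for this point.

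**Conclusion.** The gap is real. As written, one method serves untreated and freshly treated skin, with no described means of telling killing on the skin from inhibition in the sample, and the next trial depends on that distinction. The affected results are chiefly those of day 0.

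Two broader conclusions do not follow. A reader might infer that every before/after contrast is inflated. The pre-antisepsis scrapings on days 1, 3 and 5 carry no agent applied that day, and group A's post-PDT, pre-antisepsis scraping carries neither iodine nor methylene blue. A reader might also infer that all carry-over favours methylene blue PDT. Only dye residue can do so, in group B and mainly in the day 0 scraping between PDT and antisepsis. Iodine residue works against finding any PDT effect.

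The size is unknown. It depends on the suppressed share s and the true positive rate, and the documents give neither. Within the assumed ranges it runs from negligible to large enough to decide the result.

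**What to change.** In section 8.1 (skin scraping) and 8.2.1 (Microbiology):

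- Name the transport medium. Collect all scrapings (both groins, all time points, baseline included) into a medium with a neutraliser shown to work for iodine and for the dye, so that the medium does not differ between the samples compared.
- Keep group B samples in the dark until plated.
- Before the first participant, run one in-vitro spike-recovery check with staphylococci and *Cutibacterium* under four conditions: no agent, residual agent alone, neutraliser alone, and both. Report recovery for each agent.
- If the cited method or the laboratory procedures already contain such a step, state it and refer to its validation.

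Reconcile 5.2 and 8.3.2 with 7.2.1 and the table in 8.1 on whether a scraping is taken between PDT and antisepsis on day 0.

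The cost is reagents and a short bench check for about 20 participants, with no added participant procedure. Because the remaining sample is frozen for molecular work, the laboratory should confirm that the medium is compatible with the PCR. The downsides are that fewer samples may be called sterile and that results are less directly comparable with the first pilot.

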## Photodynamic treatment

### Group A (MAL group):

On day 0, a skin scraping of the groin will be performed and sent for microbiological culture. Then, 5% topical methyl aminolevulinate (MAL) as the prodrug for the photosensitizer Pp IX will be applied under occlusion in the right groin of the patient. After the incubation, the PDT will be started by irradiation of the area with day-light.

### Group B (Methylene blue)

On day 0, a skin scraping of the groin will be performed and sent for microbiological culture. Then, 5ml of the 0.01% methylene blue based photosensitizer (NF-031) will be applied for an area of 5 x 10cm in the right groin of the patient. Immediately after application, the PDT will be started by irradiation of the area with 40J/cm^2 red light from a 635 emitting LED during 4 minutes.

## Skin antisepsis

After PDT, we will perform skin antisepsis as routinely done in clinics three times with a povidone-iodine/alcohol solution (Betaseptic®, Mundipharma, Limburg, Germany) for a total duration of 3 minutes to imitate standard surgical antisepsis before a hip arthroplasty surgery.

## 8.2 Assessments of Outcomes

### 8.2.1 Assessment of Primary Outcome

What	When	How
Bacterial density and species of skin swabs	Visit 1, 2, 3 and 4	Skin swab, microbiological diagnostic methods (see below)

## Microbiology

In short, the patient's sample swabs will be streaked out onto Columbia sheep blood agar plate without antibiotics (bioMérieux, Marly-l'Etoile, France), colistin-nalidixic acid (CNA) blood agar (bioMérieux) plate for aerobic cultivation and a Brucella plate (in-house sheep blood agar plates with hemin and vitamin K1) for anaerobic cultivation using GENbag (bioMérieux). Final identification will be done by matrix-assisted laser desorption ionization-time of flight mass spectrometry spectrometry (MALDI-TOF MS) using a Bruker MALDI Biotyper. The amount of bacteria will be semiquantitative described as +, ++, +++ based on growth on agar plates. All cultured microorganisms will be stored in skim milk at -80C° for potential subsequent analysis by whole genome sequencing for analyzing the secondary outcome.

### 8.2.2 Assessment of Secondary Outcomes

To evaluate the bacterial dynamics on the skin after PDT and skin antisepsis within one week

using PCR technique in collaboration with PD Dr. sc. nat. [name], Laborleiter FAMH at the clinic for dermatology at the University Hospital of Zurich.

What	When	How
Bacterial dynamics	After termination of all study participants	Real-Time PCR

### **8.2.3 Assessment of Safety Outcomes**

#### **8.2.3.1 Serious Adverse Events**

Recording of serious adverse event (SAE) information time of onset, duration, resolution, action to be taken, assessment of intensity, and relationship with study intervention.

### **8.2.4 Assessments in Participants who prematurely Stop the Study**

Participants who are withdrawn from the study prematurely due to adverse event, will be followed-up until adverse-effects disappeared. Follow up may include but is not limited to physical examination, laboratory tests, vital signs, telephone calls. Outcomes and resolution of events will be recorded in the Case Report Forms. In case of lost to follow up, efforts will be made to contact the patient or to ascertain the vital status of the participant.

## **8.3 Procedures at Each Visit**

### **8.3.1 Screening Visit**

*Screening visit, – at least -7 days before the study start*

- Information of the study and all necessary study visits
- Check for In- and Exclusion criteria
- Enrollment if agree to participate in study
- Enter basic demographic parameters in electronic CRF (age, sex, current medications, and underlying diseases)
- Scheduling of all study visits

Duration: ca. 30 minutes

Location: Division of Infectious Diseases, University Hospital Zurich

### **8.3.2 Visit 1 = Day 0 of the study**

#### Group A (MAL group):

On day 0 with [name], a skin scraping of the groin will be performed and sent for microbiological culture. Then, 5% topical methyl aminolevulinate (MAL) as the prodrug for the photosensitizer Pp IX will be applied (5 x 10cm in the right groin) and followed by irradiation of the area with day light.

#### Group B (Methylene blue group)

On day 0 with [name], a skin scraping of the groin will be performed and sent for microbiological culture. Then, 5ml of the 0.01% methylene blue based photosensitizer (NF-031) will be applied for an area of 5 x 10cm in the right groin of the patient. Immediately after application, the photodynamic process will be started by irradiation of the area with 40J/cm^2 red light from a 635 emitting LED during 4 minutes.

Immediately after the PDT, skin antisepsis will be performed. Antisepsis of the skin is performed with a povidone-iodine/alcohol solution (Betaseptic®, Mundipharma, Limburg, Germany) and

repeated three times for a total duration of 3 minutes to imitate standard surgical antisepsis before a hip arthroplasty surgery.

For all inguinal swabs, we will use the scratching method using a scalpel as already applied in a previous study (ethical approval BASEC-Nr 2016-01017). The swabs will be sent to the microbiology laboratory of the University of Zurich for bacterial analysis (analysis under supervision of Prof. [name]).

**Duration:** 1-2 hours

**Location:** Clinic for Dermatology (located in the Circle since October 2020), University Hospital Zurich

### **8.3.3 Visit 2, 3, 4 (day 1, 3, 5)**

Skin scraping after skin antisepsis will be repeated 1, 3, and 7 days later and analyzed for bacterial cultures.

In short:

- Inguinal skin scraping
- Skin antisepsis
- Inguinal skin scraping
- Documentation of adverse effects

**Duration:** 30 - 60 minutes

**Location:** Division of Infectious Diseases, University Hospital Zurich

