### **4.3 Safety Outcomes**

Every PDT is documented as in routine clinics on a standardized protocol in the KISIM database (see appendix 1).

Clinical signs and symptoms after PDT as adverse events. We will distinguish between:

- Mild redness and pain as to be expected (yes/no)
- Advanced redness and pain more than expected (yes/no): adverse event.
  - o “More than expected” is defined, if patients needs to take more than 1 painkiller/day
- Other signs and symptoms not expected (yes/no)

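### As listed, skin reactions at follow-up are recorded after that day's scalpel sampling, with no baseline or contralateral reading scheduled, so PDT redness cannot be reliably separated from sampling and antiseptic redness

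*Combined protocol and SAP*

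**What the plan says.** **Follow-up visits.** The summary list in 8.3.3 has four steps: scraping, antisepsis, a second scraping, and "Documentation of adverse effects". Table 8.1 schedules "6. Skin antisepsis in the groin, skin scraping before and after antisepsis" at visits 1 to 4, and the next row, "7. (serious) adverse events", at the same visits. Sections 5.1 and 5.2 describe a lighter follow-up: swabbing or scraping on days 1, 3 and 5, with no repeat antisepsis stated.

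**Sampling and antisepsis.** Section 8.1 states "For all skin swabs, we will apply the scratching method using a scalpel as described previously", and 8.3.2 repeats the scalpel method for all inguinal swabs. Antisepsis is three applications of povidone-iodine/alcohol over 3 minutes in total.

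**Day 0.** Sections 5.2 and 8.3.2 state "Immediately after the PDT, skin antisepsis will be performed". Section 7.2.1 places a further scraping between PDT and antisepsis.

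**Safety outcome.** Section 4.3 defines it as "Clinical signs and symptoms after PDT as adverse events", with yes/no items. The item for more than the expected redness and pain is defined by use of more than one painkiller a day. Section 12.1.2 lists pain and redness in the source data as side effects of PDT.

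**Contralateral groin.** Sections 2.5, 5.2 and 7.1.2 describe it only in terms of swabs and antisepsis without PDT. Section 5.2 applies it to all participants, and 7.1.2 to the first 10.

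**The concern.** Scraping with a blade and applying an alcoholic antiseptic can each redden skin. If the skin is read after them, on the treated side only and with no earlier reading to compare, the entry reflects PDT, sampling and antiseptic together but is filed under PDT.

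The redness result has a real job in this trial. Section 2.1 says surgeons would hesitate to operate after the earlier MAL treatment because of erythema. Section 2.6 expects less erythema from both new regimens. Section 3.2 looks for the photosensitizer with the best trade-off between antibacterial effect and irritation. Section 2.4 makes the larger study depend on sterile cultures without side effects. Sampling redness could make a mild regimen look worse than it is, or narrow a true difference between the two regimens.

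**Working it through.** The plan gives no figure to reproduce. The check has two parts: a count of what precedes each skin record, and a test of whether PDT redness can be recovered from what is recorded.

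**1. Sampling before each listed record, treated groin**

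Inputs:
- Day 0 scrapings: 3 under 7.2.1 (before PDT, after PDT, after antisepsis), or 2 under 5.2 (before PDT, after antisepsis).
- Scrapings per follow-up visit: 2 under 8.3.3 and Table 8.1, or 1 under 5.2.
- Antisepsis: one round on day 0. Each follow-up visit adds one under 8.3.3 and Table 8.1, and none is stated in 5.2.

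| Record | Scrapings, 8.3.3 follow-up | Antisepsis rounds | Scrapings, 5.2 throughout | Antisepsis rounds |
|---|---|---|---|---|
| Day 1 | 2 or 3, plus 2 = 4 or 5 | 2 | 2 + 1 = 3 | 1 |
| Day 3 | 6 or 7 | 3 | 4 | 1 |
| Day 5 | 8 or 9 | 4 | 5 | 1 |

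At the upper end this is 3 + 2 + 2 + 2 = 9 scrapings and 4 × 3 = 12 minutes of antisepsis. If the listed order is followed, all three follow-up records come after same-day scraping under either schedule, and also after same-day antisepsis under 8.3.3 and Table 8.1.

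**2. Can PDT redness be recovered?**

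Let p be the probability of redness from PDT and s the probability of redness from sampling and antiseptic, assumed independent. On a yes/no item:

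observed rate = 1 − (1 − p)(1 − s), so p = 1 − (1 − observed)/(1 − s).

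The documents give neither p nor s. For illustration, suppose 8 of 10 participants in a group show redness:

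| Assumed s | Implied p |
|---|---|
| 0 | 1 − 0.2/1 = 0.80 |
| 0.25 | 1 − 0.2/0.75 = 0.73 |
| 0.50 | 1 − 0.2/0.50 = 0.60 |
| 0.80 | 1 − 0.2/0.20 = 0 |

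The same count fits any p from 0 to 0.80. A comparable reading on a groin that is scraped and disinfected without PDT would inform s, but none is scheduled.

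**3. The comparison between groups**

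If s is the same in both groups, the observed difference is (1 − s)(pA − pB). With assumed values pA = 0.80, pB = 0.30 and s = 0.50, the observed rates are 1 − 0.2 × 0.5 = 0.90 and 1 − 0.7 × 0.5 = 0.65. A true gap of 50 points appears as 25 points, with 10 participants per group. A shared sampling burden keeps the direction of the difference but shrinks it.

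**4. What reading first would change**

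Prior scrapings would fall to 2 or 3 on day 1, 4 or 5 on day 3 and 6 or 7 on day 5 under 8.3.3, or to 2, 3 and 4 under 5.2. No same-day scraping or antiseptic would precede the reading, but scrapings from earlier days still would.

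**The case against.** A reader might infer that the protocol requires the skin to be inspected after sampling, that it is never read at baseline or on the control side, and that PDT redness therefore cannot be told from sampling redness at all. The documents do not support that much.

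- **Order.** The list in 8.3.3 is a short summary, and its last item names a recording task. It does not say when the skin is inspected. Table 8.1 is a grid of tasks by visit and gives no timing within a visit. This stands. However, the first three items of the list are plainly sequential, and if the order is not intended, staff have no instruction on when to look.
- **Schedule.** Two scrapings plus antisepsis at follow-up is only one of two descriptions; 5.1 and 5.2 are lighter. This stands. Under either one, the list puts the record after scraping.
- **Silence.** The absence of baseline and control-side readings rests on what the visible text omits. The flow charts are not shown. The adverse event definition in 9.1 is broad enough to take in an event on the control side. Section 4.3 also refers to a routine clinic record of each PDT; the Appendix 1 example, as available, shows no skin-reaction field. So the supported statement is that no visible section schedules such a reading.
- **Impact.** No rate or duration of sampling redness is given, so a count of scrapings measures exposure and not bias. Section 4.3 treats mild redness as expected, and its more severe item depends on painkiller use, which reordering steps would leave unchanged. Section 2.4 states an intention, not a formal failure rule. Sampling in the earlier pilot is not described here, so any bias against it is unknown. All of this stands and limits the claim.
- **Rank of the outcome.** Redness is a safety item in a descriptive pilot, and the culture outcome is not affected. That is correct, but irritation is half of the trade-off that 3.2 sets out to assess.

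**Conclusion.** The point holds in a limited form. If staff follow the order listed in 8.3.3, redness at visits 2 to 4 is recorded after same-day scalpel sampling and, under 8.3.3 and Table 8.1, after antisepsis. No visible section schedules a reading before the baseline scraping, between PDT and the next scraping or antisepsis on day 0, or on the contralateral groin. Redness attributed to PDT therefore cannot be reliably separated from redness due to sampling and antiseptic using the data the plan records.

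The size of the effect is unknown. The illustrations rest on assumed rates, independence of the two causes and, for the group comparison, an equal s in both groups; they show non-identifiability and do not estimate bias. The painkiller-based item is less affected. The stronger conclusion, that separation is impossible or that late inspection is a stated rule, goes beyond the text. The change is still worth making, because it is cheap and the skin result informs both the choice of photosensitizer and the decision to proceed.

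**What to change.** 1. In 8.3.3 and Table 8.1, make the redness and pain reading the first step of each follow-up visit, before any scraping or antiseptic.
2. In 8.3.2 and Table 8.1, record the same items on day 0 before the baseline scraping, and again directly after PDT before any further scraping or antisepsis.
3. Record the same items on the contralateral groin whenever it is sampled. Report treated and contralateral readings side by side, and limit the paired contrast to days on which both groins were sampled.
4. Reconcile 5.2 (control side in all participants) with 7.1.2 (first 10 only). Under 2.7 the first 10 are group A, so on the 7.1.2 reading group B would have no contralateral side to compare. State also whether the control groin is sampled after day 0, which the text leaves open.
5. Reconcile the follow-up schedule in 5.1 and 5.2 with that in 8.3.3 and Table 8.1.
6. State that follow-up readings still come after earlier days' scrapings, so reordering reduces the sampling effect but does not remove it. Events that arise after sampling continue to be recorded as adverse events.

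Cost: a few minutes per visit and one extra eCRF line per groin, with no added visit or procedure.
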